3.0 OBJECTIVE(S) & HYPOTHESIS(ES)

3.1 Primary Objective(s) & Hypothesis(es)

Cohort 1: For subjects with recurrent and/or metastatic gastric or gastroesophageal adenocarcinoma who have progressed on at least 2 prior systemic treatments for advanced disease (3L+ subjects).

Cohort 2: For subjects with recurrent and/or metastatic gastric or gastroesophageal adenocarcinoma who have not previously received systemic therapy for advanced disease (1L subjects).

Cohort 3: PD-L1 positive subjects with recurrent and/or metastatic gastric or gastroesophageal adenocarcinoma who have not previously received systemic therapy for advanced disease (1L subjects).

- **Objective (within each Cohort 1, 2 and 3):** To determine the safety and tolerability of pembrolizumab administered at 200 mg Q3W dosing as monotherapy and in combination with cisplatin and 5-FU or cisplatin and capecitabine.
- **Objective (Cohort 1):** To estimate the Objective Response Rate (ORR) per RECIST 1.1 assessed by central imaging vendor in all subjects and in PD-L1 positive subjects.
- **Objective (Cohort 3):** To estimate the ORR per RECIST 1.1 assessed by central imaging vendor review.

3.2 Secondary Objective(s) & Hypothesis(es)

- **Objective (Cohort 1):** To estimate the Duration of Response (DOR) per RECIST 1.1 by central imaging vendor in all subjects and in PD-L1 positive subjects. Supportive analyses for this objective and the primary objective include irRECIST by central imaging vendor evaluation of ORR and DOR in all subjects and in PD-L1 positive subjects as well as RECIST 1.1 and irRECIST by central imaging vendor evaluation of DCR, PFS and OS in all subjects and in PD-L1 positive subjects.
- **Objective (Cohort 2):** To estimate antitumor activity of pembrolizumab in combination with cisplatin and 5-FU or cisplatin and capecitabine for all subjects and in PD-L1 positive subjects, determined by ORR using RECIST 1.1 by central imaging vendor. Supportive analyses for this objective include irRECIST by central imaging vendor evaluation of ORR in all subjects and in PD-L1 positive subjects as well as RECIST 1.1 and irRECIST by central imaging vendor evaluation of DOR, DCR, PFS and OS in all subjects and in PD-L1 positive subjects.
- **Objective (Cohort 3):** To estimate the Duration of Response (DOR) per RECIST 1.1 by central imaging vendor in PD-L1 positive subjects. Supportive analyses for this objective and the primary objective include irRECIST by central imaging vendor evaluation of ORR and DOR in PD-L1 positive subjects as well as RECIST 1.1 and irRECIST by central imaging vendor evaluation of DCR, PFS and OS in PD-L1 positive subjects.
- **Objective (all Cohorts):** To evaluate the relationship between PD-L1 status and efficacy endpoints in subjects receiving pembrolizumab (as monotherapy or in combination with chemotherapy) with recurrent and/or metastatic gastric or gastroesophageal junction adenocarcinoma.

3.3 Exploratory Objectives

- **Objective (all Cohorts):** To investigate the relationship between pembrolizumab treatment and biomarkers predicting response (e.g., genetic variation, serum sPDL1) utilizing newly-obtained or archival FFPE tumor tissue and/or blood (including whole blood, serum and plasma).
- **Objective (all Cohorts):** To compare performance of PD-L1 assessment in newly-obtained vs. archived tissue samples.

4.0 BACKGROUND & RATIONALE

4.1 Background

Refer to the Investigator's Brochure (IB)/approved labeling for detailed background information on MK-3475.

4.1.1 Pharmaceutical and Therapeutic Background

The importance of intact immune surveillance in controlling outgrowth of neoplastic transformation has been known for decades [1]. Accumulating evidence shows a correlation between tumor-infiltrating lymphocytes (TILs) in cancer tissue and favorable prognosis in various malignancies [2, 3, 4, 5, 6]. In particular, the presence of CD8⁺ T-cells and the ratio of CD8⁺ effector T-cells / FoxP3⁺ regulatory T-cells seems to correlate with improved prognosis and long-term survival in many solid tumors.

The programmed death-1 (PD-1) receptor-ligand interaction is a major pathway hijacked by tumors to suppress immune control. The normal function of PD-1, expressed on the cell surface of activated T-cells under healthy conditions, is to down-modulate unwanted or excessive immune responses, including autoimmune reactions. PD-1 (encoded by the gene *Pdcd1*) is an Ig superfamily member related to CD28 and CTLA-4 which has been shown to negatively regulate antigen receptor signaling upon engagement of its ligands (PD-L1 and/or PD-L2) [7, 8]. The cytoplasmic tail of PD-1 contains 2 tyrosine-based signaling motifs, an immunoreceptor tyrosine-based inhibition motif (ITIM) and an immunoreceptor tyrosine-based switch motif (ITSM). Following T-cell stimulation, PD-1 recruits the tyrosine phosphatases SHP-1 and SHP-2 to the ITSM motif within its cytoplasmic tail, leading to the dephosphorylation of effector molecules such as CD3 ζ , PKC θ , and ZAP70 which are involved in the CD3 T-cell signaling cascade [7, 9, 10, 11]. The mechanism by which PD-1 down modulates T-cell responses is similar to, but distinct from that of CTLA-4 as both molecules regulate an overlapping set of signaling proteins [12, 13]. PD-1 was shown to be expressed on activated lymphocytes including peripheral CD4⁺ and CD8⁺ T-cells, B-cells, T regs and Natural Killer cells [14, 15]. Expression has also been shown during thymic development on CD4-CD8- (double negative) T-cells as well as subsets of macrophages and dendritic cells [16]. The ligands for PD-1 (PD-L1 and PD-L2) are constitutively expressed or can be induced in a variety of cell types, including non-hematopoietic tissues as well as in various tumors [17, 18, 19, 12]. Both ligands are type I transmembrane receptors containing both IgV- and IgC-like domains in the extracellular region and contain short cytoplasmic regions with no known signaling motifs. Binding of either PD-1 ligand to PD-1 inhibits T-cell activation triggered through the T-cell receptor. PD-L1 is expressed at low levels on various non-hematopoietic tissues, most notably on vascular endothelium, whereas PD-L2 protein is only detectably expressed on antigen-presenting cells found in lymphoid tissue or chronic inflammatory environments. PD-L2 is thought to control immune T-cell activation in lymphoid organs, whereas PD-L1 serves to dampen unwarranted T-cell function in peripheral tissues [12]. Although healthy organs express little (if any) PD-L1, a variety of cancers were demonstrated to express abundant levels of this T-cell inhibitor. PD-1 has been suggested to regulate tumor-specific T-cell expansion in patients with melanoma [20]. In

gastric cancer PD-L1 and PD-L2 overexpression have recently been associated with EBV-positive tumors [21]. This suggests that the PD-1/PD-L1 pathway plays a critical role in tumor immune evasion and can be an attractive target for therapeutic intervention.

Pembrolizumab is a potent and highly selective humanized monoclonal antibody (mAb) of the IgG4/kappa isotype designed to directly block the interaction between PD-1 and its ligands, PD-L1 and PD-L2. Pembrolizumab has an acceptable preclinical safety profile and is in clinical development as an intravenous (IV) immunotherapy for advanced malignancies. Keytruda® (pembrolizumab) is indicated for the treatment of patients across a number of indications. For more details on specific indications refer to the Investigator's Brochure.

4.1.2 Pre-clinical and Clinical Trials

Therapeutic studies in mouse models have shown that administration of antibodies blocking PD-1/PD-L1 interaction enhances infiltration of tumor-specific CD8+ T-cells and leads ultimately to tumor rejection, either as a mono-therapy or in combination with other treatment modalities. Anti-mouse PD-1 or anti-mouse PD-L1 antibodies have demonstrated anti-tumor responses as a mono-therapy in models of squamous cell carcinoma, pancreatic carcinoma, melanoma and colorectal carcinoma. Blockade of the PD-1 pathway effectively promoted CD8+ T-cell infiltration into the tumor and the presence of IFN- γ , granzyme B and perforin, indicating that the mechanism of action involved local infiltration and activation of effector T-cell function in vivo [22, 23, 24, 25, 26, 27]. Experiments have confirmed the in vivo efficacy of PD-1 blockade as a mono-therapy as well as in combination with chemotherapy in syngeneic mouse tumor models (see the IB).

Clinical trials have demonstrated efficacy in multiple solid tumor indications and hematologic malignancies. Refer to pembrolizumab IB for study details.

4.1.3 Ongoing Clinical Trials

Ongoing clinical trials are being conducted in advanced melanoma, NSCLC, a number of advanced solid tumor indications and hematologic malignancies. For study details please refer to the IB.

Preliminary interim data are available from a cohort of gastric adenocarcinoma patients studied in trial KN012 [28]. KEYNOTE-012 trial is a multi-cohort Phase 1b study of which one cohort enrolled subjects with recurrent or metastatic gastric or GEJ adenocarcinoma that expressed PD-L1 ($\geq 1\%$ by immunohistochemistry). This cohort enrolled 39 subjects (19 from Asia and 20 outside Asia), 67% of whom had received 2 or more prior chemotherapy lines. The primary efficacy endpoint was objective response rate (ORR). Despite the heavily pre-treated patient population, Pembrolizumab monotherapy demonstrated an interim ORR of 33% by RECIST v.1.1 per investigator review (95% confidence interval [CI] 19.1%, 50.2%; all partial responses). The interim disease control rate (DCR) was 41% (95% CI 25.6%, 57.9%). ORR was similar in patients from Asia and outside of Asia, while the DCR was numerically higher in Asia. Responses were observed across all lines of treatment. It should be noted that in the non-Asia group, patients had less

prior therapy relative to the Asian patients, and that ORR in later line patients ($\geq 3L$) was higher in the Asian group (1 PR/7 patients in the non-Asia group, 4 PR/13 patients in the Asia group). As of the data cut-off date of 14-NOV-2014, the median duration of response was 24 weeks (6 months). Based on preliminary data, there appears to be a correlation between response and degree of PD-L1 positivity.

In these gastric cancer patients in KN012, single-agent pembrolizumab at 10 mg/kg Q2W was generally well tolerated, with the type, severity, and frequency of adverse events similar to that observed in other indications (see the IB for information about adverse events in other indications). There was 1 death reported in the gastric cancer cohort. This patient had adverse events of tracheomalacia (Grade 3) and hypoxia (Grade 5). The investigator considered the Grade 5 hypoxia to be related to study treatment.

4.2 Rationale

4.2.1 Rationale for the Trial and Selected Subject Population

KEYNOTE 059 (KN059) is a Phase II, 3-cohort, single arm, open-label trial of pembrolizumab alone or in combination with 5-FU (or capecitabine) and cisplatin in subjects with advanced gastric or gastroesophageal junction adenocarcinoma (note that term gastric cancer in this protocol will refer to both gastric adenocarcinoma as well as gastroesophageal junction adenocarcinoma). It will be conducted as 3 separate cohorts: a cohort of subjects who have progressed on at least 2 prior systemic treatments for advanced disease (3L+ subjects), and 2 cohorts of subjects who have not previously received systemic therapy for advanced disease (1L subjects) - one of which consist of subjects receiving pembrolizumab in combination with different chemotherapy regimens and one will consist of subjects receiving pembrolizumab monotherapy.

The PD-L1 IHC assay planned for use in this trial will be a clinical assay with the potential to be further developed and registered. In KN012 a PD-L1 prototype IHC assay was used that is different than the assay planned for KN059. The definition of PD-L1 IHC positive in KN012 is $\geq 1\%$ tumor cell staining or stromal staining. The definition of PD-L1 positive in this trial, KN059, will be generally equivalent to the definition used in KN012 [28]; the actual percent positive staining required may be different with the updated assay currently being developed for use in the trial.

4.2.1.1 Cohort 1: 3L and Later Subjects

Treatment options are limited for 3L+ gastric cancer subjects, especially in western countries, with no approved or recommended treatments. In East Asian countries, single agent chemotherapy (taxane or irinotecan) is commonly used. There is minimal data on the response to treatment in 3L or later. One study conducted at a single site in Korea reported a response rate of 3.8% in 2L or later patients receiving weekly paclitaxel [29]. Overall survival was generally similar between the 2L and 3L+, while PFS was worse in the later line (3L+) patients, with a median PFS of 1.7 months. However, these had poorer performance scores (ECOG 2-3) relative to that planned in this study. A low ORR was also observed in

the REGARD study in which 2L patients were randomized to either ramucirumab or best supportive care [30]. In contrast to the previous study, patients in REGARD had better performance scores (ECOG 0 or 1) yet the ORR was still 3% in both treatment groups. Based on the improved overall survival observed in the ramucirumab group, ramucirumab as a single agent was approved in the United States for treatment of 2L gastric cancer.

The gastric cancer proof-of-concept from KN012 data was obtained in PD-L1 positive subjects only; no data is currently available regarding the performance of pembrolizumab in PD-L1 negative subjects. Therefore, the primary efficacy hypothesis for this cohort will be in the PD-L1 positive population. However, due to the limited treatment opinions currently available, late line PD-L1 negative subjects may benefit from pembrolizumab. The performance of pembrolizumab in these subjects will be explored in approximately 25 PD-L1 negative subjects and a futility analysis will be conducted based on ORR at 9 weeks, with a futility criterion of the upper bound of the 95% confidence interval for ORR <20%. Should the efficacy of pembrolizumab be non-futile in this subgroup, then enrollment of PD-L1 negative subjects will continue and an assessment of all-comers with regard to PD-L1 will be performed at the end of the study.

This will be operationalized by enrolling up to ~40 all-comer subjects, as the PD-L1 IHC assay will not be available for subject selection at the initiation of the trial (it will be available approximately 3 months after study initiation). Assuming a 40% PD-L1 positive rate based on the data from KN012, this will give approximately 25 PD-L1 negative subjects. At this point the PD-L1 subject selection assay is expected to be available, and enrollment of PD-L1 negative subjects will stop until after the futility assessment in the subjects determined to be PD-L1 negative from these initial ~40 all-comers.

As of 19-OCT-2015, the interim analysis has been performed and the external DMC has reviewed the data. The futility criterion was not met (please see Section 8.7 for the futility rule) and the DMC recommended that enrollment of PD-L1 negative subjects can be resumed. The enrollment for all subjects will stop when at least 80 all-comer (PD-L1 positive or negative) subjects meeting the revised eligibility criteria are enrolled. According to the enrollment rate projection, a total of approximately 130 subjects will be enrolled before the revised eligibility criteria are implemented. It is estimated that the overall sample size for Cohort 1 is approximately 210.

4.2.1.2 Cohort 2: 1L Subjects Receiving Combination Treatment

Based on the results of KN012, pembrolizumab is expected to have meaningful activity in both early and late lines of therapy. Current 1L treatments for metastatic gastric cancer consist of combination chemotherapy, most often consisting of a doublet containing a platinum agent and a fluoropyrimidine agent. Western patients in good condition may receive a triple combination in which an agent from a third class (e.g., taxane or anthracycline) is added. Response rates of combination chemotherapies in these patients are generally in the 40% range. It is possible that maximal treatment benefit can be obtained by adding pembrolizumab to doublet chemotherapy in 1L subjects. Cohort 2 of this study is designed to assess the safety and tolerability of this combination regimen, with cisplatin and

5-FU as the doublet chemotherapy regimen. Sites in Japan will also administer pembrolizumab in combination with cisplatin and capecitabine as the doublet regimen. This assessment will support the use of these regimens in future global clinical trials. Based on safety and tolerability, the doses of the chemotherapies may be reduced for individual subjects or an entire cohort. This information will inform dose selection for future combination trials.

The subject population for this cohort will be all-comers with respect to the PD-L1 selection assay. It is possible that PD-L1 negative subjects could benefit from addition of pembrolizumab to chemotherapy, and the primary safety objective is not expected to be impacted by PD-L1 status. In addition, an all-comer population will necessitate a shorter enrollment time and therefore earlier availability of the key safety data to support future trials.

4.2.1.3 Cohort 3: 1L Subjects Receiving Pembrolizumab Monotherapy

The final cohort in this study will be PD-L1 positive 1L gastric cancer subjects who will receive pembrolizumab monotherapy. The objective of this cohort is to provide further data assessing the performance of pembrolizumab monotherapy in this population to support future trials of single-agent pembrolizumab in early-line patients. In KN012, the current ORR in subjects who were treatment naïve or have had one prior line of therapy, there are 3 partial responders in 9 subjects (with 3 additional subjects having stable disease). Cohort 3 of this study will provide data in an additional 25 subjects to better understand efficacy. PD-L1 positive only subjects will be enrolled in this cohort, since there are no current data in PD-L1 negative subjects and these subjects may be less likely to benefit from pembrolizumab monotherapy. Since the ORR of standard treatments for these subjects is in the range of 40%-50%, this efficacy objective is to show an ORR >35%, which would suggest that pembrolizumab may be similar to, or better than, standard of care, and support future trials with a monotherapy regimen in these subjects (e.g., pembrolizumab could have a similar ORR but long duration of response which could translate into a superior survival benefit).

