8.3 Hypotheses/Estimation

This is an estimation study. Objectives of the study are stated in Section 3.0.

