Cohort 2 (1L gastric cancer subjects/combination treatment): There will be approximately 18 subjects enrolled for all-comer population. [Table 17](#) shows the two-sided 95% CI of AE rate with 18 subjects.

Table 17 Two-sided 95% CI of AE incidence rate with 18 Subjects

Number of AE	AE incidence rate estimates	95% CI of incidence rate (%)
2	11.1%	(1.4, 34.7)
4	22.2%	(6.4, 47.6)
5	27.7%	(9.7, 53.5)
7	38.9%	(17.3, 64.2)
9	50.0%	(26.0, 73.9)

Cohort 3 (1L gastric cancer subjects/monotherapy): There will be ~25 PD-L1 positive subjects enrolled in Cohort 3. Using Bayesian sample size methods and assuming a uniform prior for the response rate (beta-binomial prior with beta (1, 1)), if we observe no more than 8 responders (i.e. observed ORR \leq 32%), there is \geq 77% posterior probability that the true ORR is less than 40% (ORR from Standard of Care).

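### Does Cohort 3's stated aim of an ORR above 35% undermine its estimation objective and its 40% benchmark?

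*Combined protocol and SAP*

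**What the plan says.** Protocol Section 4.2.1.3 gives the reasoning for Cohort 3. It puts the ORR of standard first-line treatment at 40% to 50%, then states "this efficacy objective is to show an ORR >35%, which would suggest that pembrolizumab may be similar to, or better than, standard of care". The same sentence says that such a result would support later monotherapy trials. It adds that a comparable ORR with longer-lasting responses might still turn into a survival advantage. The section describes the cohort's purpose as follows: "Cohort 3 of this study will provide data in an additional 25 subjects to better understand efficacy".

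The formal objective in Section 3.1 has no threshold: "To estimate the ORR per RECIST 1.1 assessed by central imaging vendor review". Section 8.3 says "This is an estimation study", and Section 3.3 of the supplemental SAP repeats it. Section 8.6.1 specifies a point estimate with a Clopper-Pearson 95% interval.

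Section 8.9, repeated in Section 3.9 of the supplemental SAP, says "There will be ~25 PD-L1 positive subjects enrolled in Cohort 3". With a uniform prior it then makes one statement: 8 or fewer responders would give at least a 77% "posterior probability that the true ORR is less than 40% (ORR from Standard of Care"). It gives no figure for 9 or more responders, and it does not mention 35%.

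**The concern.** Three sections seem to set Cohort 3 three different tasks: to show an ORR above 35%, to estimate the ORR, and to compare it with 40%. The 35% bar lies below the quoted standard range, yet passing it is said to suggest parity or better. Section 8.9 quantifies only the disappointing outcome and does not say what 9 or more responders would establish.

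ORR is the primary efficacy endpoint of this cohort, and the result is meant to inform whether first-line monotherapy trials go ahead. If 9/25 were announced as meeting the objective and read as comparable to standard treatment, the claim would go further than the plan's own model allows.

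**Working it through.** **Inputs.** n = 25 (Sections 4.2.1.3 and 8.9, the latter as an approximate number); prior Beta(1,1) and reference rate 40% (Section 8.9); bar 35% and standard range 40% to 50% (Section 4.2.1.3).

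**Where the bar falls.** 0.35 × 25 = 8.75. So 8/25 = 32% is the highest count below the bar and 9/25 = 36% is the lowest count above it.

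**The plan's own figure.** After x responders the posterior is Beta(1 + x, 26 − x), and P(ORR < 0.40 | x) equals P(Bin(26, 0.40) ≥ x + 1). At x = 8 the posterior is Beta(9, 18) and the probability is 0.774. Fewer responders give a higher value, so the stated figure of at least 77% is reproduced.

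**The same model at higher counts.**

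| Responders of 25 | Observed ORR | P(true ORR < 40%) |
|---|---|---|
| 8 | 32% | 0.774 |
| 9 | 36% | 0.636 |
| 10 | 40% | 0.479 |
| 11 | 44% | 0.326 |

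At 9/25 the posterior is Beta(10, 17). It gives P(true ORR > 35%) = 0.573 and P(true ORR > 30%) = 0.770. The Clopper-Pearson 95% interval is 18.0% to 57.5%.

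**Sensitivity to n, since 25 is approximate.** P(true ORR < 40%) at the lowest count above 35%:

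| n | Count | P(true ORR < 40%) |
|---|---|---|
| 23 | 9 | 0.51 |
| 24 | 9 | 0.58 |
| 25 | 9 | 0.64 |
| 26 | 10 | 0.54 |
| 27 | 10 | 0.60 |

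Of these sizes, n = 25 gives the least favourable value. A Jeffreys prior at 9/25 gives 0.65, so the choice of prior matters little.

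**How often 9 or more of 25 would occur.** P(X ≥ 9) is 0.15 at a true ORR of 25%, 0.32 at 30%, 0.53 at 35%, 0.73 at 40% and 0.87 at 45%. At a true ORR of 40% the count is therefore missed with probability 1 − 0.73 = 0.27.

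**The stricter reading.** If showing an ORR above 35% meant an exact 95% lower bound above 35%, 15/25 would be needed: the lower bound is 34.9% at 14/25 and 38.7% at 15/25. P(X ≥ 15) is 0.10 at a true ORR of 45% and 0.21 at 50%. No section of the plan sets such a rule, so these are not properties of this trial.

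**Which planned output uses 35%?** None. Sections 8.1, 8.6.1 and 8.9 and the matching sections of the supplemental SAP report the ORR with an exact interval, set no success criterion for Cohort 3, and plan an interim analysis for Cohort 1 only.

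**The case for a change.** The best case for a change is that the rationale is what readers remember. It calls passing 35% an efficacy objective, and it allows the words "which would suggest that pembrolizumab may be similar to, or better than, standard of care" to be attached to a result that the plan's own model places below 40% more often than not. For n from 23 to 27 that probability never falls below one half at the lowest qualifying count. No margin is given for similarity, the hedging does little to support the claim of being better at 36%, and Section 8.9 is silent on the side that the rationale relies on. New wording and a three-line posterior table would cost almost nothing.

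Part of this stands. The verb in Section 4.2.1.3 does not match Section 3.1, Section 8.9 covers only the low side, and 9/25 is weak evidence.

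The rest carries less weight.

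- P(ORR < 40%) tests whether the regimen is at least equal to the bottom of the standard range. The text claims only that it may be similar, in support of further trials, and it gives a reason based on response duration. A bar slightly below the standard is normal for that purpose.
- Three separate goals is too strong a reading. The cut at 8 responders in Section 8.9 is exactly the point at which 35% is missed, so that statement describes failing the bar and adds no separate aim.
- The figure of 0.64 belongs to the single lowest qualifying count. Any threshold looks weak at its boundary, and one more responder brings the probability below one half.
- Anyone can obtain the high-side posteriors from the model that Section 8.9 already specifies.

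**Conclusion.** No change to the plan is needed. The mismatch between a threshold in the rationale and an estimation objective is a wording slip in background text. An analyst following Section 8 or the supplemental SAP would report the same estimate and interval whether or not the sentence were corrected. At the least favourable qualifying result, that report is 36% with an interval of 18.0% to 57.5%. The interval spans the whole 40% to 50% standard range and reaches well below it, so it supports no firm claim of parity and does not exclude similarity.

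Using 40% in place of 35% as the informal bar would raise the lowest qualifying count from 9 to 10 of 25 if a rate of exactly 40% qualifies. That moves P(true ORR < 40%) at the boundary from 0.64 to 0.48. It is a preference about phase II screening and corrects no error.

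This conclusion assumes that the 35% is read as an observed rate, that about 25 subjects are enrolled (0.51 to 0.64 at the boundary for 23 to 27), and that the result is presented with its interval, as planned. It would be different if 35% were used as a formal success criterion, but neither document does so.
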